##### **IV.c. Research Plan.**

Patients with T2DM admitted with acute or chronic medical illnesses or for elective and emergency surgical illness or trauma would be considered candidates in this study. The goal of insulin therapy is to maintain a fasting and pre-meal BG<140 mg/dL while avoiding hypoglycemia. Diabetic patients admitted to general medical or surgery areas with a BG > 140 mg/dL and < 400 mg/dL will be randomized (using a randomization table) to:

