**IV.d. Basal Bolus Insulin Protocol.**

Patients will be started on basal bolus insulin therapy as previously reported (6; 7; 11; 13). In brief, subjects treated with insulin prior to admission will receive 80% of the outpatient insulin dose. Insulin-naïve patients will discontinue oral agents and will receive a starting total daily dose (TDD) of insulin of 0.4 U/kg/day for BG between 140-200 mg/dL and 0.5 U/kg/day for BG between 201-400 mg/dL. The starting TDD will be 0.3 U/kg/day in patients  $\geq 70$  yrs or with an eGFR < 60 ml/min. Half of TDD will be given as glargine or detemir once daily and half as meal time insulin (aspart or lispro) divided in three equal doses before meals. Insulin dose will be adjusted daily to maintain a fasting and pre-dinner BG between 100-140 mg/dL (6; 7).

Supplement insulin given as aspart or lispro will be given following a “supplemental insulin scale” protocol (6; 7; 27). Patients randomized to Group 1 will receive supplements to correct BG > 140 mg/dL, and those in Group 2 will not receive supplements except for correction of hyperglycemia (BG>260 mg/dL). Corrective doses for bedtime in group 1 will be given for BG > 220 mg/dL.

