**BEDTIME. Give half of Supplemental Sliding Scale Insulin**

Blood Glucose (mg/dL)	Sensitive	Usual	Resistant
< 260	0	0	0
261-300	2	3	5
301-350	3	4	6
351-400	4	5	7
> 400	5	6	8

The attending physician may change insulin dose as his/her discretion in the presence of hypoglycemia (BG <70 mg/dL) or severe hyperglycemia (BG >350 mg/dL). In addition, the attending and/or study physician may consider using the total supplemental insulin dose, patient's nutritional intake, and results of BG testing to adjust insulin regimen.

**Blood glucose monitoring.** BG will be measured before each meal, at bedtime and 3 AM (or every 6 hours if a patient is not eating) using a glucose meter. In addition, blood glucose will be measured at any time if a patient experiences symptoms of hypoglycemia or if requested by the treating physician. The nursing staff or a research team staff will record all glucose readings in the hospital's blood glucose flow-sheet (chart).

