## **V. METHODS and PROCEDURES APPLIED to HUMAN SUBJECTS:**

**V.a. Subject Population/Inclusion Criteria.** We plan to study a total of 250 male and female patients with a known history of T2DM for >3 months, age 18-80 yr, treated with either diet alone, any combination of oral antidiabetic agents, non-insulin injectables or insulin therapy. Subjects must have a BG >140 mg and <400 mg/dL without laboratory evidence of diabetic ketoacidosis (28).

**Exclusion Criteria.** Subjects with hyperglycemia without a history of diabetes, acute critical illness admitted to the ICU or expected to require ICU admission; receiving continuous insulin infusion, clinically relevant hepatic disease, corticosteroid therapy, creatinine  $\geq 3.5$  mg/dL and/or GFR <30, subjects unable to sign consent, and pregnancy which will be excluded by a urine pregnancy test.

**V.b. Study Sites:** The study will be conducted at Grady Memorial Hospital and Emory University Hospitals (EUH and EUHM).

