## **VI. CLINICAL MANAGEMENT GUIDELINES**

**V.I.a. Treatment of Hypoglycemia.** Hypoglycemia, defined as a BG level < 70 mg/dL will be treated following standard hypoglycemia protocols available at our institutions (6; 7; 29).

**V.I.b. Assessment and Monitoring of Hospital Complications and Mortality.** The research team will follow patients daily in order to determine presence of infectious and non-infectious complications. Nosocomial infections will be diagnosed based on standardized CDC criteria (30).

**VII. Data Analysis.** The primary endpoint of this study is mean fasting BG concentration between treatment groups. We set the equivalence margin in our non-inferiority hypothesis for comparing treatment effect as 18 mg/dL (1 mmol/l). Based on previous studies (6; 7), we anticipate a standard deviation of mean fasting BG~50 mg/dL. With a one-sided, two-sample t-test, 123 subjects would be required for each group to achieve 80% power to detect non-inferiority. Here we conservatively set the significance level as 0.025 to ensure sufficient power when a two-sided test is used for the primary outcome, we will perform cross-sectional analyses using one-way ANOVA or linear models, followed by repeated measures ANOVA or linear models to estimate difference between treatment groups while simultaneously examining mean fasting BG across multiple days during treatment. Similar analyses will be conducted for continuous secondary outcomes. Chi-square tests (or Fisher's Exact test), Logistic regression, and Poisson regression will be conducted to analyzed discrete secondary outcomes. A p-value of <0.05 is considered significant. We expect a very low attrition rate in the proposed study. Therefore, a total of 250

patients (125 patients per group) will be recruited in this pilot study. The proposed methods will be implemented by SAS (v9.2).

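### Allocation is described only as a randomization table, and the primary analysis names no hospital or prior-insulin term, so precision available at no cost in patients is left unused and concealment cannot be verified

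*Combined protocol and SAP*

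**What the plan says.** Section IV.c (Research Plan) holds the whole description of allocation: patients "will be randomized (using a randomization table) to" Group 1 or Group 2. No section says how the table was generated, who holds it, whether assignments are concealed, or whether there are blocks or strata.

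On setting, Section V.b states: "The study will be conducted at Grady Memorial Hospital and Emory University Hospitals", and names two Emory hospitals in parentheses. Section IX (Timetable) speaks of two hospitals. Blinding status is not stated. The two groups have different correction scales in plain view, and the Group 2 section adds: "The attending physician may change insulin dose as his/her discretion".

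On pre-admission treatment, Section V.a admits patients "treated with either diet alone, any combination of oral antidiabetic agents, non-insulin injectables or insulin therapy". Section IV.d then applies different starting rules. For home-insulin users, "subjects treated with insulin prior to admission will receive 80% of the outpatient insulin dose". Insulin-naive patients follow a weight-based rule: they "will receive a starting total daily dose (TDD) of insulin of 0.4 U/kg/day for BG between 140-200 mg/dL", with a higher glucose band and a separate rule by age and eGFR.

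Section VII (Data Analysis) plans one-way ANOVA or linear models, followed by repeated-measures versions. It names no covariate.

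**The concern.** There are two separate issues.

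The first is concealment. Treatment is open in practice. Research staff screen patients and investigators or coordinators take consent (Sections XVII and XXII). Some exclusion criteria in Section V.a call for judgement, such as an expected need for ICU care or clinically relevant liver disease. The stated hypothesis is that correction doses will not improve control. If recruiters could learn the next assignment, enrolment could be steered, and neither the sample size nor the t-test protects against that. The plan does not say what prevents it.

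The second is precision. Pre-admission insulin use must be recorded to choose the starting-dose rule, and it may well be related to inpatient glucose. An analysis that leaves it out carries that variation as noise, in a non-inferiority comparison planned with power close to 80%.

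**Working it through.** **Inputs from Section VII:** margin 18 mg/dL, SD 50 mg/dL, one-sided alpha 0.025, power 80%, 123 per group required, 125 recruited. The SD is for mean fasting glucose. Section IV.b names mean daily glucose as the primary outcome, which is a separate matter.

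**Assumed, not in the documents:** share on home insulin p = 20-50%; difference d in mean glucose between home-insulin users and others = 10-40 mg/dL.

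**1. The plan's own figure.** The normal approximation gives 122 per group. The noncentral t calculation gives 123 (power 80.3%), so the stated 123 reproduces. At 125 per group, power is 80.9% by the t-test. The standard error of the arm difference is 50 × √(2/125) = 6.3 mg/dL, so the 95% half-width is 1.96 × 6.3 = 12.4 mg/dL.

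**2. Chance imbalance without strata.** The SD of the between-arm difference in the home-insulin share is √(2p(1−p)/125).

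| p | SD of difference (points) | Chance of a gap ≥ 10 points |
|---|---|---|
| 20% | 5.1 | 4.8% |
| 30% | 5.8 | 8.4% |
| 40% | 6.2 | 10.6% |
| 50% | 6.3 | 11.4% |

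A 10-point gap moves the arm difference by 0.10 × d, which is 1 to 4 mg/dL. The 95% range of the shift, 1.96 × SD × d, runs from ±1.0 mg/dL (p = 20%, d = 10) to ±5.0 mg/dL (p = 50%, d = 40).

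**3. That shift is not additional to the planned error.** Its variance is 2p(1−p)d²/125. The variance of the arm difference is 2 × 2500/125. The ratio is p(1−p)d²/2500, which is the share of outcome variance that prior insulin explains. The shift is thus one component of the 12.4 mg/dL half-width and already sits inside the SD of 50.

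**4. Gain from adjustment.** Residual SD = 50 × √(1 − p(1−p)d²/2500). Sample size and power below use the normal approximation.

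| p | d (mg/dL) | Variance removed | Residual SD | Required n per arm | Power at 125 per arm |
|---|---|---|---|---|---|
| none | none | 0 | 50.0 | 122 | 81% |
| 20% | 10 | 0.6% | 49.8 | 121 | 81.5% |
| 30% | 20 | 3.4% | 49.2 | 118 | 82.5% |
| 40% | 30 | 8.6% | 47.8 | 111 | 84.6% |
| 50% | 40 | 16.0% | 45.8 | 102 | 87.4% |

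Any gain from a hospital term comes on top; the documents give nothing from which to size it.

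**5. Foreseeability.** This depends on concealment and blocking. With a concealed, unblocked list, past assignments say nothing about the next. With fixed blocks of known size b and open treatment, the share of assignments that is certain in advance is 1/(b/2 + 1): 50% for b = 2, 33% for 4, 25% for 6, 20% for 8. If recruiters can see the table, the share is 100%. The documents do not say which case applies.

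**The case against.** The strongest reply is that most of this is missing description rather than a demonstrated flaw. Section IV.c is written in the passive and names no user or holder of the table, and the text neither states nor rules out strata. A reader might infer that allocation can be foreseen because no strata are named. That does not follow: strata have no bearing on it, and a concealed, unblocked list is the hardest to predict. This objection stands. What remains is that foreknowledge is not excluded.

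A reader might also set the ±1 to ±5 mg/dL shift against the 18 mg/dL margin as a further threat to the non-inferiority conclusion. Step 3 of the working shows why that fails: the planned 123 per group already allows for it.

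The assumed inputs are open to challenge too. Both arms state the same glucose bands for daily dose adjustment, which would tend to narrow differences that arise from the starting dose, so the true d could be near zero and the gain negligible. Nor does prior insulin alone fix the starting dose; weight, glucose, age and eGFR set it for insulin-naive patients. Both points stand.

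Finally, at 125 per arm a covariate in the model recovers nearly all the precision without stratified allocation, and Section VII already permits linear models. That also stands, and it makes the model term the main change and stratification its companion. It does not answer the point, because Section VII names no covariate and leaves an unadjusted one-way ANOVA as an option.

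**Conclusion.** The point holds as an inexpensive improvement to the analysis plus a gap in the description of allocation. It does not show bias, and it does not call for more patients.

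On precision, adjusting for pre-admission insulin use removes about 1-16% of the variance and takes power at 125 per arm from about 81% to between 81.5% and 87%. This rests on 20-50% home-insulin use and a 10-40 mg/dL difference, neither of which the documents give. At the low end the gain is trivial, but so is the cost.

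On allocation, concealment, blocking and strata are not described in a trial that is open in practice and recruits at more than one hospital. No size can be put on selection through foreknowledge, because nothing in the documents shows that it would happen. That the trial is open is itself an inference from the two visible scales.

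**What to change.** In Section VII, replace the unadjusted one-way ANOVA with a linear model prespecified to contain treatment, hospital and pre-admission insulin use (yes/no), and carry the same factors into the repeated-measures model.

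In Section IV.c, state that the list is computer-generated in permuted blocks of varying size, stratified by the same two factors. State who generates and holds it, and that each assignment is released by a concealed method only after consent and eligibility are recorded. Reconcile Sections V.b and IX on the number of hospitals first. Three hospitals give 3 × 2 = 6 strata, or about 250/6 ≈ 42 patients per stratum on average; two give 4 strata, or about 62.

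The cost is a few lines of text and generation of the list. No patients are added, and prior insulin use has to be recorded anyway to choose the starting-dose rule. The documents name no system for releasing assignments, so the sponsor has to choose one, and the cost of that step cannot be read from the plan.

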**Group 1. Basal bolus insulin regimen *with* corrective doses of aspart/lispro insulin for BG > 140 mg/dL (n = 125).**

**Group 2. Basal bolus insulin regimen *without* corrective doses of aspart/lispro insulin except for BG > 260 mg/dL (n = 125).**

The primary medical team (PMT) will decide on the treatment for the surgical and other medical problem(s) for which patients are admitted. The study team will provide recommendations for discharge as outlined below but will leave it up to the discretion of the PMT. The PMT can also decide the medical treatment at discharge including the use of insulin or oral antidiabetic agent(s), patient's discharge orders and referral to the diabetes clinic at discharge.

**IV.d. Basal Bolus Insulin Protocol.**

Patients will be started on basal bolus insulin therapy as previously reported (6; 7; 11; 13). In brief, subjects treated with insulin prior to admission will receive 80% of the outpatient insulin dose. Insulin-naïve patients will discontinue oral agents and will receive a starting total daily dose (TDD) of insulin of 0.4 U/kg/day for BG between 140-200 mg/dL and 0.5 U/kg/day for BG between 201-400 mg/dL. The starting TDD will be 0.3 U/kg/day in patients  $\geq 70$  yrs or with an eGFR < 60 ml/min. Half of TDD will be given as glargine or detemir once daily and half as meal time insulin (aspart or lispro) divided in three equal doses before meals. Insulin dose will be adjusted daily to maintain a fasting and pre-dinner BG between 100-140 mg/dL (6; 7).

Supplement insulin given as aspart or lispro will be given following a “supplemental insulin scale” protocol (6; 7; 27). Patients randomized to Group 1 will receive supplements to correct BG > 140 mg/dL, and those in Group 2 will not receive supplements except for correction of hyperglycemia (BG>260 mg/dL). Corrective doses for bedtime in group 1 will be given for BG > 220 mg/dL.

**Group 1. Basal bolus regimen with corrective doses of rapid-acting insulin prior to meals.**

**Patients Treated with Insulin Prior to Admission**

- Subjects receiving insulin therapy will receive 80% of the total daily outpatient insulin dose. For subjects receiving glargine, detemir, regular, lispro, glulisine or aspart, the total daily insulin dose prior to admission will be switched to basal insulin (glargine or detemir)/ meal time insulin (aspart/lispro) combination on a unit-for-unit basis.
- Half of total daily dose will be given as basal insulin (glargine or detemir) insulin and half as meal time insulin (aspart/lispro) insulin.
- Basal insulin (glargine or detemir) insulin will be given once daily, at the same time of the day.
- Patients will receive the full-dose of basal insulin (glargine or detemir) (even if NPO) the day of surgery or diagnostic procedure(s).
- Meal time insulin (aspart/ lispro) insulin will be given in three equally divided doses before each meal. To prevent hypoglycemia, if a subject is not able to eat, the dose of meal time insulin (aspart/lispro) will be held.

### **Patients Treated with Oral Agents Prior to Admission**

- Oral antidiabetic drugs (sulfonylureas, repaglinide, nateglinide, metformin, pioglitazone, DPP4 inhibitors) and non-insulin injected antidiabetic drugs (pramlinitide, exenatide, liraglutide) will be discontinued on admission.
- **Starting total daily insulin dose:**
  - 0.4 units per kilogram of body weight per day when the blood glucose concentration at randomization is between 140-200 mg/dL.
  - 0.5 units per kilogram of body weight per day blood glucose concentration at randomization is between 201-400 mg/dL
  - The starting insulin TDD will be reduced to 0.3 units per kg in patients  $\geq 70$  years of age and/or with an eGFR  $< 60$  ml/min.
- Half of total daily dose will be given as basal insulin (glargine or detemir) and half as meal time insulin (aspart/lispro).
- Basal insulin (glargine or detemir) will be given once daily, at the same time of the day.
- Patients will receive the full-dose of basal insulin (glargine or detemir) insulin (even if NPO) the day of surgery or diagnostic procedure(s).
- Meal time insulin (aspart/lispro) will be given in three equally divided doses before each meal. To prevent hypoglycemia, if a subject is not able to eat, the dose of aspart/lispro will be held.

**Supplemental insulin.** Aspart/lispro insulin will be administered following the “supplemental insulin scale” protocol.

- If a patient is able and expected to eat all or most of his/her meals, supplemental aspart or lispro insulin will be administered before each meal and at bedtime following the “usual” dose of the supplemental insulin scale protocol.
- If a patient is not able to eat, supplemental aspart or lispro insulin will be administered every 6 hours following the “sensitive” dose of the supplemental insulin scale protocol.

### **Insulin adjustment.**

- Daily insulin dose will be adjusted as follow:
  - If the fasting and/or pre-dinner BG is between 100 - 140 mg/dL in the absence of hypoglycemia the previous day: no change
  - If the fasting and/or pre-dinner BG is between 140 - 180 mg/dL in the absence of hypoglycemia: increase basal insulin by 10% every day
  - If the fasting and/or pre-dinner BG is  $>180$  mg/dL in the absence of hypoglycemia the previous day: increase basal insulin dose by 20% every day
  - If the fasting and/or pre-dinner BG is between 70 - 99 mg/dL in the absence of hypoglycemia: decrease TDD (basal and prandial) insulin dose by 10% every day
  - If a patient develops unexplained hypoglycemia (BG  $<70$  mg/dL), the insulin TDD (basal and prandial) should be decreased by 20%.

**Supplemental Insulin (aspart/lispro) prior to meals:**

**BEFORE MEAL, Supplemental Sliding Scale Insulin (number of units) - Add to scheduled insulin dose.**

Blood Glucose (mg/dL)	Sensitive	Usual	Resistant
≤ 140	0	0	0
>141-180	2	3	4
181-220	3	4	6
221-260	4	5	8
261-300	5	6	10
301-350	6	8	12
351-400	7	10	14
> 400	8	12	16

**BEDTIME. Give half of Supplemental Sliding Scale Insulin.**

Blood Glucose (mg/dL)	Sensitive	Usual	Resistant
<221	0	0	0
221-260	1	2	4
261-300	2	3	5
301-350	3	4	6
351-400	4	5	7
> 400	5	6	8

The patient's inpatient primary medical or surgical team may change insulin dose at their discretion in the presence of hypoglycemia (BG <70 mg/dL) or severe hyperglycemia (BG >350 mg/dL). In addition, the attending and/or study physician may consider using the total supplemental insulin dose, patient's nutritional intake, and results of BG testing to adjust insulin regimen.

**Blood glucose monitoring.** BG will be measured before each meal, at bedtime and/or 3 AM (or every 6 hours if a patient is not eating) using a glucose meter. In addition, blood glucose will be measured at any time if a patient experiences symptoms of hypoglycemia or if requested by the treating physician. The nursing staff or a research team staff will record all glucose readings in the hospital's blood glucose flow-sheet (electronic chart).

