### **Patients Treated with Oral Agents Prior to Admission**

- Oral antidiabetic drugs (sulfonylureas, repaglinide, nateglinide, metformin, Actos, DPP4 inhibitors) and non-insulin injected antidiabetic drugs (pramlinitide, exenatide) will be discontinued on admission.
- **Starting total daily insulin dose:**
  - 0.4 units per kilogram of body weight per day when the admission and/or blood glucose concentration at randomization is between 140-200 mg/dL
  - 0.5 units per kilogram of body weight per day when the admission and/or mean blood glucose concentration is between 201-400 mg/dL
  - The starting insulin TDD will be reduced to 0.3 units per kg in patients  $\geq 70$  years of age and/or with an eGFR  $< 60$  ml/min.
- Half of total daily dose will be given as basal insulin (glargine or detemir) and half as meal time insulin (aspart or lispro).
- Basal insulin (glargine or detemir) will be given once daily, at the same time of the day.
- Patients will receive the full-dose of basal insulin (glargine or detemir) (even if NPO) the day of surgery or diagnostic procedure(s).
- Meal time insulin (aspart/lispro) will be given in three equally divided doses before each meal. To prevent hypoglycemia, if a subject is not able to eat, the dose of aspart/lispro will be held.

**Supplemental insulin.** Aspart or lispro insulin will be administered following the “supplemental insulin scale” protocol before meals.

- If a patient is able and expected to eat all or most of his/her meals, supplemental (aspart or lispro) insulin will be administered before each meal following the “usual” dose of the supplemental insulin scale.
- If a patient is not able to eat, supplemental (aspart/lispro) insulin will be administered every 6 hours following the “sensitive” dose of the supplemental insulin scale protocol.

**Insulin adjustment.** Daily insulin dose will be adjusted as follow:

- If the fasting and/or pre-dinner BG is between 100 - 140 mg/dL in the absence of hypoglycemia the previous day: no change
- If the fasting and/or pre-dinner BG is between 140 - 180 mg/dL in the absence of hypoglycemia: increase basal insulin by 10% every day
- If the fasting and/or pre-dinner BG is >180 mg/dL in the absence of hypoglycemia the previous day: increase basal insulin dose by 20% every day
- If the fasting and/or pre-dinner BG is between 70 - 99 mg/dL in the absence of hypoglycemia: decrease basal and prandial insulin TDD by 10% every day

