**Insulin supplementation (aspart or lispro) prior to meals:**

**BEFORE MEAL, Supplemental Sliding Scale (number of units) - Add to scheduled insulin dose.**

Blood Glucose (mg/dL)	Sensitive	Usual	Resistant
< 260	0	0	0
261-300	5	6	10
301-350	6	8	12
351-400	7	10	14
> 400	8	12	16

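### The bedtime Sensitive doses do not follow the halving their heading orders, and no text says which table governs 6-hourly doses in patients who cannot eat

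*Combined protocol and SAP*

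**What the plan says.** Section IV.d prints two supplemental scales for each group, each with Sensitive, Usual and Resistant columns.

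- **Before-meal scale.** Group 1's is headed "BEFORE MEAL, Supplemental Sliding Scale Insulin (number of units) - Add to scheduled insulin dose" and Group 2's "BEFORE MEAL, Supplemental Sliding Scale (number of units) - Add to scheduled insulin dose".
- **Bedtime scale.** In both groups the heading is "BEDTIME. Give half of Supplemental Sliding Scale Insulin". For Group 1 the introduction to IV.d adds "Corrective doses for bedtime in group 1 will be given for BG > 220 mg/dL", and the bedtime table accordingly shows 0 units below 221 mg/dL.
- **Patients who eat, Group 1.** "supplemental aspart or lispro insulin will be administered before each meal and at bedtime following the" Usual column.
- **Patients who cannot eat.** Group 1: "If a patient is not able to eat, supplemental aspart or lispro insulin will be administered every 6 hours following the" Sensitive dose of the scale. Group 2: "If a patient is not able to eat, supplemental (aspart/lispro) insulin will be administered every 6 hours following the" Sensitive dose of the scale. Neither sentence names a table.

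For a patient who cannot eat, IV.d also has the scheduled mealtime insulin held, and it has basal insulin given in full on the day of surgery or a procedure, fasting or not.

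**The concern.** There are two linked problems.

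First, the bedtime heading states a rule (half) and the cells beneath it should follow that rule. The Usual and Resistant columns do, apart from one half-unit of rounding. The Sensitive column follows a different rule.

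Second, Sensitive is the column that the written rules reserve for patients who cannot eat. It appears in two tables with different values. One table is labelled for mealtimes and the other for bedtime, and the 6-hourly schedule is tied to neither.

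The correction dose is the randomised intervention, so two staff members reading the same page should reach the same dose. The patients concerned are foreseeable, since elective and emergency surgical patients are eligible (IV.c). Hypoglycemia is a secondary outcome (IV.b), and severe hypoglycemia feeds a stopping rule (VIII.d).

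**Working it through.** **Inputs.** All are doses in units from the before-meal and bedtime tables of IV.d. Group 2 prints the same values as Group 1 in every band above 260 mg/dL, and 0 below that.

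**Step 1: does bedtime equal half of before-meal?** Formula: expected bedtime dose = before-meal dose / 2. Sensitive column:

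| BG (mg/dL) | Before meal | Half | Printed bedtime | Before meal minus bedtime | Bedtime / before meal | Fits half? |
|---|---|---|---|---|---|---|
| 221-260 (Group 1 only) | 4 | 2 | 1 | 3 | 25% | under no rounding |
| 261-300 | 5 | 2.5 | 2 | 3 | 40% | only rounded down |
| 301-350 | 6 | 3 | 3 | 3 | 50% | exactly |
| 351-400 | 7 | 3.5 | 4 | 3 | 57.1% | only rounded up |
| > 400 | 8 | 4 | 5 | 3 | 62.5% | under no rounding |

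The difference is exactly 3 units in all five Group 1 rows and all four Group 2 rows.

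The other two columns, for comparison:

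- Resistant: 8, 10, 12, 14, 16 halved is 4, 5, 6, 7, 8. This is what is printed, in 5 of 5 rows.
- Usual: 5, 6, 8, 10, 12 halved is 2.5, 3, 4, 5, 6. Printed: 2, 3, 4, 5, 6. It is exact in 4 of 5 rows, and the fifth is rounding.

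The irreconcilable rows are therefore 221-260 (1 unit below half) and above 400 (1 unit above half). The two middle rows need opposite rounding. A round-to-even convention would do that, but the plan states no rounding rule, and none reaches the two outer rows.

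**Step 2: what dose does a 6-hourly reading carry in a patient who cannot eat?** Read the Sensitive column from each table in turn:

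| BG (mg/dL) | Group 1: before-meal or bedtime table | Group 2: before-meal or bedtime table |
|---|---|---|
| 141-180 | 2 or 0 | 0 or 0 |
| 181-220 | 3 or 0 | 0 or 0 |
| 221-260 | 4 or 1 | 0 or 0 |
| 261-300 | 5 or 2 | 5 or 2 |
| 301-350 | 6 or 3 | 6 or 3 |
| 351-400 | 7 or 4 | 7 or 4 |
| > 400 | 8 or 5 | 8 or 5 |

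If the bedtime heading is followed instead of its cells, 221-260 in Group 1 and above 400 in both groups acquire a third figure (2 and 4 units).

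**Step 3: what does this do to the contrast per reading?** From the table above, the planned Group 1 minus Group 2 difference across 141-180, 181-220 and 221-260 is 2, 3, 4 units under the before-meal table and 0, 0, 1 under the bedtime table. Above 260 mg/dL the two arms carry the same doses and the same ambiguity. Going from a single reading to the trial would need the proportion of readings taken in non-eating patients, which the plan does not give.

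**The case against.** The case on the other side is substantial.

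**The mismatch is small and partly rare.** Three of five rows can be read as half if rounding is allowed, and the other two are off by 1 unit. The 221-260 row has no counterpart in Group 2. Readings above 400 mg/dL are put at 0.08% in the preliminary data and 0.1% in the background, and VIII.b expects fewer than 1% of patients above 350. In the presence of readings above 350 the treating team may change the dose anyway. All of this stands and limits the size of the first problem. It does not make heading and cells agree. A deliberately cautious Sensitive column does not explain the pattern either, since the top row exceeds half.

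**The wording leans towards the before-meal table.** The bedtime heading treats the supplemental scale as the parent and bedtime as a reduction of it. The sentences on non-eating patients refer to the scale, not to the reduction, and Group 2's lead-in ties the scale to mealtimes. So the two readings are not equally supported. But Group 1's lead-in has no such words, and Group 2's may describe timing only. The before-meal table is to be added to a scheduled dose, and in these patients that dose is held. On this reading the bedtime Sensitive column has no stated user. IV.d also cites published trials for the scale; whether they settle the matter cannot be seen from the documents.

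**A stronger reading is not supported.** A reader might set the 3-unit gap against the 5 to 9 units/day of supplement in Table 1 and infer a large distortion of the trial. That compares one reading in a non-eating patient with an average daily dose over a whole trial arm. A reader might also infer that the whole Sensitive bedtime column is wrong; only two rows are irreconcilable with the heading.

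**Conclusion.** The point holds as an internal contradiction plus an unresolved reference. The contradiction is two bedtime Sensitive rows that disagree with their heading by 1 unit each, in opposite directions: one in Group 1 only, one in both groups. The unresolved reference is that non-eating patients are sent every 6 hours to a column that exists in two tables 3 units apart in every band from 221 mg/dL up, and 2 to 3 units apart at 141-220 in Group 1.

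This rests on the tables as printed. A fault in reading the file is unlikely, because the Group 2 tables repeat the same values in every shared band. No bias in the treatment comparison and no excess of hypoglycemia is claimed, since the share of non-eating patients is unknown and the ambiguity above 260 mg/dL is common to both arms. The plan's sample size and analysis are not affected. It should still be corrected, because it concerns delivery of the randomised intervention in patients who may be receiving full basal insulin without eating.

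**What to change.** The sponsor's clinical team should reconcile, in IV.d, the two supplemental-insulin paragraphs with the four before-meal and bedtime tables, so that:

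1. the bedtime heading and the Sensitive cells say the same thing, with any rounding rule stated;
2. the table that governs each 6-hourly reading in a patient who cannot eat is named;
3. the wording is the same in Group 1 and Group 2, apart from the glucose threshold that defines the arms.

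Which values stand is a clinical decision, and none is proposed here. The cost is wording in the protocol and the order set. Sample size, data collection and analysis do not change.
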